7.5.4 Efficacy assessments

7.5.4.1 Adaptive behavior

The VABS-II is assessed at Screening, Baseline (within 2 weeks prior to first SOBI003 infusion) and at Week 24. The screening assessment is used to determine patient eligibility in terms of developmental age.

The patients' ability to cope with changes, to demonstrate independence and to learn new skills are assessed by use of the Expanded Interview Form of the VABS-II. This measures five competence domains: communication, socialization, daily living skills, motor skills and an adaptive behavior composite of the first four domains.

The VABS-II is assessed by parent/caregiver interviews performed by child development specialists/psychologists with prior experience of MPS IIIA patients. Prior to study initiation, additional study-specific assessment training is provided in order to reduce between-site variability. Every effort will be made to have the same parent/caregiver interviewed at each assessment time point (i.e., at Screening, Baseline and Week 24). In addition, each patient's parent/caregiver should preferably have the same interviewer throughout the study in order to reduce potential variability.

The developmental age at Screening is determined as the mean of the subdomain age-equivalent scores including the communication, socialization, daily living skills, and motor skills domains.

The adaptive behavior age-equivalent score is determined as the mean of the subdomain age-equivalent scores including the communication, socialization, and daily living skills (thus, excluding the motor skills domains).

Completed assessment forms will be sent to a central reader (NeuroCog Trials), for data quality assurance of completed assessment forms, calculation of final scores and determination of Age Equivalence scores, and data management.

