7.5.4.3 Language

Language is assessed at Baseline and at Week 24.

Expressive and receptive language are assessed by the BSID-III language module and the VABS-II communication domain. In addition, written language is assessed by the VABS-II communication domain.

For those patients taking the KABC-II for cognitive assessment, the Expressive Vocabulary from the KABC-II will be applied to assess language development.

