7.5.4.4 Motor function

Motor function is assessed at Baseline and at Week 24.

Fine and gross motor skills are assessed by the BSID-III motor function module and the VABS-II motor skills domain.

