4.1 Overall study design and plan

This is an open-label, non-controlled, parallel, sequential ascending multiple-dose, multicenter study to assess the dose related safety, tolerability, pharmacokinetics (PK), and pharmacodynamics (PD) of SOBI003 in pediatric MPS IIIA patients. An overview for the study design is presented in [Figure 1](#).

In February 2020, Sobi decided to discontinue the SOBI003 program. At the time of the decision, 3 patients had been included in Cohort 1 and 3 patients in Cohort 2 of the FIH study (SOBI003-001). All patients had been enrolled in the Extension study (SOBI00-002) and will have the possibility to continue their treatment for a total of two years. Thus, Cohort 3 in the FIH study (SOBI003-001) will not be started. Statistical analysis for the FIH study (SOBI003-001) CSR will be done for Cohort 1 and 2.

Figure 1 Overview for study design for Study SOBI003-001

SOBI003 is administered as weekly intravenous (i.v.) infusions over a period of time of 4 hours. The study treatment period comprises 24 weekly infusions. Prior to initiation of each infusion, the patients are pre-treated with a single dose of non-sedative antihistamine. If infusion-related reactions occur, then the infusion duration may be expanded up to 24 hours and supportive medication may be administered, at the discretion of the investigator.

The study is planned to consist of 3 dose cohorts, each comprising 3 patients, provided that no significant safety concern arise. An additional cohort comprising 3 patients may be added, if deemed necessary to more accurately characterize the safety, tolerability, PK or PD.

The screening visit can be performed up to 12 weeks prior to the first SOBI003 infusion. At the screening visit, the MPS IIIA diagnosis is verified and the genotype is determined at a central laboratory. Patients are assigned to a dose cohort in consecutive order as the eligibility criteria have been confirmed, with prioritization of the younger patients.

Treatment initiations will be staggered within each cohort in order to be able to observe, interpret and treat possible adverse reactions and to ensure that such reactions can be dealt with promptly. For each cohort, safety review committee (SRC) meetings are scheduled approximately 3 weeks after completion of the 3rd patient's 4th dose administration. Based on the safety, immunogenicity, PK and PD data, the SRC will determine what dose to apply in the next cohort.

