13.1.1 VABS-II

For this study, the VABS-II assesses adaptive behavior in 4 competence domains (communication, socialization, daily living skills, and motor skills). The domain scores yield an adaptive behavior composite of the 4 domains (4). The VABS-II is assessed by parent/caregiver interviews performed by child development specialists/ psychologists with prior experience of MPS IIIA patients. A series of age-equivalent questions obtains a decreasing score between "4" and "0" or "DK" (don't know) based on how independently the individual is able to perform the behavior (i.e., 4 = "performs almost always independently", 0 = "never performs/never performs independently") is answered. The developmental age at Screening will be determined as the mean of the subdomain AEQ scores including the communication, socialization, daily living skills, and motor skills domains

The adaptive behavior AEQ and composite score will be obtained with the mean of the subdomain scores communication, socialization, daily living skills and motor skills for patients aged up to 6 years and 11 months. For patients aged 7 years and above, the adaptive behavior composite score will be obtained with the 3 subdomain scores communication, socialization, and daily living skills.

The VABS-II will be assessed at Screening, Baseline (within 2 weeks prior to 1st SOBI003 infusion) and at Week 24 (see **Table 1**). Each patient's parent/caregiver should preferably have the same interviewer throughout the study in order to reduce potential variability. Completed

assessment forms will be sent to a central reader (NeuroCog Trials), for data quality assurance of completed assessment forms, calculation of final scores and determination of AEq scores, and data management.

Changes from baseline (as defined in Section 8.4.3) will be calculated at Week 24.

13.1.2 **BSID-III**

The BSID-III is a standard series of measurements used primarily to assess the development of infants and toddlers. Children are assessed in the 5 key developmental subtests of cognitive, language, social-emotional, motor and adaptive behavior (5). For each developmental subtest the patient must respond to a series of questions with a score of “1” or “0” based on the successful completion (“1”) of a task. Total raw scores for each subtest can be obtained by adding all scores of the questions in the subtest.

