13.2.2 Adaptive behavior

The endpoint relating to the 5th secondary objective will be obtained with the adaptive behavior AEq as assessed by VABS-II (see Section [13.1.2](#)). Change from Baseline (as defined in Section [8.4.3](#)) will also be assessed at Week 24.

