16.2.3 Summary of HS concentrations in serum, urine, and CSF

HS serum, urine, and CSF concentration data will be summarized by treatment using the following descriptive statistics: n, number and % of LLOQ, arithmetic mean, SD, CV%, minimum, median and maximum, Q1 and Q3. In addition, results will be presented by demographic characteristics, e.g., age group and bodyweight, as applicable.

Samples taken outside the allowed time windows may be excluded from summarization. This will be determined prior to database lock.

Mean \pm SD HS concentrations in serum, urine and CSF vs Week number profiles will be presented, combining the curves for all dose levels within the same figure.

The HS levels including change from baseline will also be summarized by visit and time point using descriptive statistics. The HS change from baseline will also be presented as percentages.

The conventions presented in [Table 9](#) for PK parameters will also be used for the presentation of the descriptive statistics of HS serum concentrations.

17 Changes from protocol

- Schedule of events tables [Table 1](#), [Table 2](#), [Table 3](#), and [Table 7](#) have been updated according to protocol clarification letters
- According to the protocol linear mixed models were planned to be used to assess the PD effect of different dose levels of SOBI003 on HS levels in CSF, serum, and urine. Because of the discontinuation of the program modelling will be not be performed.

18 References

- 1 ICH Topic E9. Statistical principles for clinical trials (CPMP/ICH/363/96). March 1998: <http://www.ich.org/products/guidelines/efficacy/article/efficacy-guidelines.html>
- 2 Committee on Professional Ethics of the American Statistical Association. Ethical Guidelines for Statistical Practice dated 2016. Available from: <http://www.amstat.org/ASA/Your-Career/Ethical-Guidelines-for-Statistical-Practice.aspx>
- 3 Van de Kamp JJP, Niermeijer MF, von Figura K and Giesberts MAH. Genetic heterogeneity and clinical variability in the Sanfilippo syndrome (types A, B and C). *Clinical Genetics*. 1981; 20: 152-60.
- 4 Community-University Partnership for the Study of Children, Youth, and Families (2011). Review of the Vineland Adaptive Behavior Scales-Second Edition (Vineland-II). Edmonton, Alberta, Canada.
- 5 NCS Pearson (2006). Bayley Scales of Infant and Toddler Development-Third Edition. Green Valley Drive Bloomington, Minnesota, USA.

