14.2 EFFICACY DATA

14.2.1 Vineland Adaptive Behaviour Scales (VASB-II)

Table 14.2.1.1	Vineland Adaptive Behaviour Scales (VASB-II) - Communication: Summary by Visit and Change from Baseline – Full Analysis Set
Table 14.2.1.2	Vineland Adaptive Behaviour Scales (VASB-II) - Daily Living Skills: Summary by Visit and Change from Baseline – Full Analysis Set
Table 14.2.1.3	Vineland Adaptive Behaviour Scales (VASB-II) - Socialization: Summary by Visit and Change from Baseline – Full Analysis Set
Table 14.2.1.4	Vineland Adaptive Behaviour Scales (VASB-II) - Motor Skills: Summary by Visit and Change from Baseline – Full Analysis Set
Table 14.2.1.4	Vineland Adaptive Behaviour Scales (VASB-II) – Adaptive Behaviour Composite Standard Score and Age-equivalent (AEq): Summary by Visit and Change from Baseline – Full Analysis Set

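### SAP 13.1.1 puts the motor domain into the VABS-II adaptive behavior age-equivalent, a secondary endpoint that the protocol defines without motor, and Section 17 does not report the change

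*SAP*

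**What the plan says.** Protocol 7.5.4.1 sets out separate VABS-II quantities. Developmental age at Screening averages subdomain age-equivalents over four domains, motor included. The adaptive behavior composite also covers four domains. The adaptive behavior AEq averages subdomain age-equivalents over "communication, socialization, and daily living skills (thus, excluding the motor skills domains" only.

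Protocol 6.2.1 and SAP 3.4.2 name the change in that AEq at Week 24 as the only endpoint of the 5th secondary objective. The composite score and VABS-II motor function are separate exploratory endpoints.

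SAP 13.1.1 keeps the four-domain developmental age. It then gives a combined rule: "adaptive behavior AEQ and composite score will be obtained with the mean of the subdomain scores communication, socialization, daily living skills and motor skills". This rule runs to age 6 years 11 months. A three-domain alternative starts at age 7 and mentions the composite only.

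SAP 13.2.2 states: "The endpoint relating to the 5th secondary objective will be obtained with the adaptive behavior AEq as assessed by VABS-II". It gives no definition of its own and refers the reader to Section 13.1.2, which describes the BSID-III.

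In the SAP table index (14.2.1) the AEq appears in one title, "Adaptive Behaviour Composite Standard Score and Age-equivalent (AEq"). No title names a three-domain AEq.

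SAP Section 17 lists two changes from the protocol. One is the updated schedule and PK sampling tables. The other is the dropped mixed models for heparan sulfate: "Because of the discontinuation of the program modelling will be not be performed". Neither concerns VABS-II scoring.

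**The concern.** The protocol's explicit parenthesis shows that leaving motor out of the AEq was intended. The SAP merges the AEq with the composite and so brings motor back in. If the derivation is programmed from the SAP, the study report will show a secondary endpoint under the protocol's name with a different content, and nothing will tell the reader. Motor change would also count twice: once in its own exploratory endpoint and once inside the adaptive behavior endpoint.

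**Working it through.** **Who is affected.** Inputs: maximum age at first infusion 72 months (inclusion criterion 3); 24 weeks of treatment; SAP limit 6 years 11 months = 6 × 12 + 11 = 83 months.

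Oldest age at Week 24 = 72 + 168/30.44 = 77.5 months. Two further weeks of delay give 72 + 182/30.44 = 78.0 months. Both are below 83, so the motor-inclusive rule covers every eligible patient at Baseline and at Week 24, and the age-7 branch applies to nobody. SAP 4.1 records that "3 patients had been included in Cohort 1 and 3 patients in Cohort 2", so the definition differs for all 6.

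**Effect on the change score.** Let dO be the Week 24 change in the mean non-motor AEq, dM the change in the motor AEq, and w the weight of motor in the SAP mean.

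- Protocol: change = dO
- SAP: change = (1 − w) × dO + w × dM
- Difference = w × (dM − dO)

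A constant gap between motor and the other domains therefore cancels from the change score. It does not cancel from the by-visit values: at w = 1/4, an assumed gap of 12 months moves the reported AEq by 12/4 = 3 months.

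**The weight.** The SAP does not say how subdomains and domains are weighted, so both readings are shown.

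- Equal weight per domain: w = 1/4.
- Equal weight per subdomain: motor has two (fine and gross, Protocol 7.5.4.4: "Fine and gross motor skills are assessed by the BSID-III motor function module and the VABS-II motor skills domain"). Communication has three (expressive, receptive and written, Protocol 7.5.4.3: "written language is assessed by the VABS-II communication domain"). The documents do not count the subdomains of socialization and daily living skills; three each is assumed. Then w = 2/(2 + 3 + 3 + 3) = 2/11 = 0.182.

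**Results for assumed values of dM − dO.** The sign follows the sign of dM − dO.

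| dM − dO (months) | w = 1/4 | w = 2/11 |
|---|---|---|
| 1 | 0.25 | 0.18 |
| 3 | 0.75 | 0.55 |
| 6 | 1.50 | 1.09 |

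One patient with a 3-month difference, in a cohort of 3 whose other two patients have none, moves the cohort mean by 0.75/3 = 0.25 month or 0.55/3 = 0.18 month.

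**The case against.** The strongest reply is that this is loose drafting, not a changed analysis. The protocol itself builds the composite from four domains, and the SAP's age-7 branch names the composite alone. The sentence averages subdomain scores, whereas the one before it averages subdomain age-equivalents. The paragraph may describe composite scoring with the AEq added carelessly. That is plausible, but the sentence is still the only derivation the SAP gives for the AEq, and nothing elsewhere overrides it.

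Second, both documents assign the final scores and age-equivalents to a central reader. If the reader applies the protocol rule, the reported figure may be right despite the SAP. The reader's rule is not in the documents. This point stands as a reason to check, not as a reason to leave the text.

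Third, the SAP plans separate tables for each of the four domains and patient listings, so motor can be seen on its own. That helps, although the domain table titles do not say whether they show age-equivalents, and the headline endpoint would still be mislabelled.

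Fourth, Section 17 mentions protocol clarification letters that are not available here. It ties them only to the schedule and PK sampling tables. Section 17 also omits other differences, such as the timing of data monitoring committee meetings. The omission is therefore no evidence of intent, but the definition remains undeclared in the SAP.

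Finally, the consequence is modest: efficacy is descriptive, there are three patients per cohort, and the program has been discontinued. The choice of neurocognitive test, which also uses the AEq, is not a further consequence. By the time of this SAP all patients had entered the extension study, and the Baseline test is meant to be reused at Week 24. This limits the severity and does not remove the conflict.

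**Conclusion.** The concern holds. The SAP's AEq includes motor and the protocol's does not, the difference covers every patient and assessment, and the SAP does not declare it. Under the assumed weights and assumed differences in change of 1 to 6 months, a patient's Week 24 change shifts by 0.18 to 1.50 months in either direction. Where motor and non-motor change agree, the shift is zero. The actual size and direction cannot be known from the documents. It should be fixed because it alters the definition of a named secondary endpoint, but no hypothesis test or decision rule depends on it.

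**What to change.** 1. In SAP 13.1.1, split the sentence. Define the adaptive behavior AEq as the mean of the subdomain age-equivalents in communication, socialization and daily living skills, without motor, at all ages, as in Protocol 7.5.4.1. Keep the four-domain rule for the exploratory composite only.
2. In SAP 13.2.2, change the cross-reference from 13.1.2 to 13.1.1.
3. Label the AEq output as three-domain.
4. Confirm that the central reader's scoring follows the same rule.

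If a four-domain AEq is really intended, list and justify it in Section 17 and report the protocol-defined AEq beside it.

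The cost is one sentence, one derivation, one cross-reference, one output label and one query to the central reader. The subdomain scores are already collected.

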13.1.4 PedsQL

The PedsQL™ is a modular approach to measuring health-related quality of life in healthy children and adolescents and those with acute and chronic health conditions. PedsQL includes the following scales covering 4 domains: physical, emotional, social and school functioning (7). Questions and scales vary for the different age categories (13 to 24 months, 2 to 4 years, and 5 to 7 years). Also, the PedsQL™ Family Impact Module will be completed with the following 8 domains: physical, emotional, social, and cognitive functioning, as well as communication, worry, daily activities, and family relationships.

For each of the domains, a series of questions will be answered and then rated with a categorical score between “4”, “3”, “2”, “1” or “0” based on how much of a problem the patient has in solving the task described by the question. A summary score is subsequently obtained for each patient so that higher scores indicate better health-related quality of life.

The total score of the PedsQL (for both the assessment of the child’s quality of life and of caregiver burden) will be obtained with the following steps:

1. Transform score. Items are reversed scored and linearly transformed to a 0-100 scale as follows: 0=100, 1=75, 2=50, 3=25, 4=0
2. Each scale score will be calculated as the sum of the transformed individual score items, divided by the number of non-missing items. Note that a scale score is only calculated if at least 50% of the associated items are non-missing.
3. Total score = sum of all the items over the number of items.

The PedsQL will be assessed at Baseline and at Weeks 12 and 24. Changes from Baseline (as defined in Section 8.4.3) will be calculated at Week 12 and 24. The PedsQL will only be listed.

13.1.5 CSHQ

The CSHQ is a psychological questionnaire designed to examine sleep behaviors in children and adolescents. The CSHQ includes items related to a number of key sleep domains that represent typical sleep complaints in this age group (8).

The scores for each of the items are assigned corresponding to the number of times per week that the sleeping behavior occurs, between “3” (usually, 5 to 7 times), “2” (sometimes, 2 to 4 times), or “1” (rarely, 0 to 1 times). A number of items on the questionnaire are reverse-scored, so that higher scores consistently indicate problem behaviors.

Two additional items are added to the original CSHQ questionnaire to further characterize common MPS IIIA specific issues with sleep, i.e., disruptive behavior at night and dangerous behavior at night. This CSHQ will capture the child’s sleep habits during the past week.

Items will be combined into 8 subscales. The total sleep disturbance score will be obtained with the sum of the score of all items of the 8 subscales. Note that a subscale score will only be calculated if at least 50% of the associated items are non-missing and the total sleep disturbance score will only be calculated if all subscales have at least 50% non-missing items. For the remaining missing values, each item will be imputed with the mean of the subscale.

The CSHQ will be completed at Baseline and prior to the infusions at Weeks 12 and 24. The CSHQ will be recorded in the eCRF. Changes from Baseline (as defined in [8.4.3](#)) will be calculated at Week 12 and 24.

13.2 Secondary efficacy endpoints

13.2.1 Neurocognitive developmental age

The neurocognitive developmental age (months) will be derived on the basis of the BSID-III cognitive total score and BSID-III age-normative data.

The neurocognitive developmental age (months) will be derived from the mean AEq scores on the NVI of the KABC-II, where an AEq score is the average score for a particular age.

The DQ is calculated as the AEq for cognitive development divided by the chronological age for the child multiplied by 100, i.e.

$$DQ = 100 * AEq / age$$

For patients completing an assessment of both BSID-III and KABC-II, the BSID-III score will be used as a basis for calculating the DQ of neurocognitive development at baseline. A calibration of overlapping AEq scores between BDID-III and KABC-II will be done to assess if a patient outgrows the BSID-III test during the duration of the study. If confirmed, assessments of KABC-II will form the basis for calculating DQ of neurocognitive development for remaining study assessments.

Changes from Baseline (as defined in Section [8.4.3](#)) will be assessed at Week 24.

13.2.2 Adaptive behavior

The endpoint relating to the 5th secondary objective will be obtained with the adaptive behavior AEq as assessed by VABS-II (see Section [13.1.2](#)). Change from Baseline (as defined in Section [8.4.3](#)) will also be assessed at Week 24.

13.2.3 Magnetic resonance imaging

The endpoint relating to the 6th secondary objective will be obtained with the gray matter volume assessed by brain volumetric MRI. Changes from Baseline (as defined in Section [8.4.3](#)) will be assessed at Week 24.

13.2.4 Quality of life and caregiver burden

The endpoint relating to the 7th secondary objective will be obtained with the parent proxy-report format of the PedsQL Version 4.0 used to assess the child's quality of life, and the family impact module of the PedsQL Version 2.0 used to assess the caregiver burden. The PedsQL version (i.e.,

infant/toddler/young children) will be selected on the basis of the chronological age of the patient. Both questionnaires will be recorded in the eCRF.

